6. STUDY POPULATION

6.1. Inclusion Criteria

Patients meeting all of the following criteria must be enrolled in the study:

1. All patients must have histologically or cytologically confirmed, advanced, relapsed or metastatic gastric or gastroesophageal junction adenocarcinoma.
2. Patient is ≥ 18 years of age (or country's legal age of majority if the legal age was > 18 years) at the time of obtaining informed consent.
3. Patient must have one of the following diagnoses to be eligible for enrollment into cohorts:
 - A. Cohort 1: Checkpoint inhibitor naïve Epstein-Barr Virus negative (EBV-) gastric cancer patient who has had a disease progression after at least 2 prior systemic treatments for advanced or metastatic gastric cancer
 - B. Cohort 2: Checkpoint inhibitor naïve Epstein-Barr virus positive (EBV+) gastric cancer patient (as determined by standard methods, e.g. EBER ISH or LMP-1 IHC) who had at least 1 prior systemic treatment for advanced or metastatic gastric cancer
4. Patient has an Eastern Cooperative Oncology Group (ECOG) performance status of 0 or 1 and has a life-expectancy ≥ 3 months.
5. Patient's interval from prior to the first study dose is at least 4 weeks for systemic anticancer therapy including investigational agents (or at least 5 half-lives for investigational/ non-cytotoxic agents, whichever is longer. Upon discussion with the Medical Monitor, fewer than stated wash-out period may be allowed provided that the patient has adequately recovered from any clinically relevant toxicity).
6. Patient must have at least one measurable lesion at baseline by computed tomography(CT) or magnetic resonance imaging (MRI) per Response Evaluation Criteria in Solid Tumors (RECIST v1.1) Lesions situated in a previously irradiated area are considered measurable if progression has been demonstrated in such lesions.
7. Demonstrate adequate organ function as defined in Table 1.1:1. All screening labs should be performed within 14 calendar days prior to the first study dose.
8. Patient must be willing and able to provide tissue from a newly-obtained biopsy of a tumor lesion not previously irradiated (unless subsequent progression demonstrated). In addition, patient must be willing to provide a tumor biopsy while on treatment at Cycle 2 day 15 (± 3 days) and may be asked to provide additional biopsies at other timepoints such as the time of discontinuation due to progression. Newly-obtained tissue will be from the stomach and/or gastroesophageal junction or a metastatic location. The post-treatment biopsy specimens should be preferred to collected from the same lesion that was biopsied pre-treatment.

Note: Newly obtained is defined as a specimen obtained up to 6 weeks (42 days) prior to initiation of treatment on Day 1 (Cycle 1) and with no additional anti-cancer treatment having been given after the specimen was obtained. To confirm eligibility, preferred to use archival tissue, but newly obtained biopsy specimens may be replaced for patient unable to submit

archival tissue samples. Newly-obtained (FFPE block or tissue in formalin solution) or archived specimens (FFPE block) are preferred to slides.

Note: The preferred submitting specimen is the FFPE block. If submitting unstained cut slides, newly cut slides should be submitted to the testing laboratory. Details pertaining to tumor tissue submission can be found in the Laboratory Manual.

9. For female patient of childbearing potential should have a negative serum pregnancy test within 14 calendar days prior to the first study dose.
10. A female participant is eligible to participate if she is not pregnant, not breastfeeding, and at least one of the following conditions applies: a) Not a woman of childbearing potential (WOCBP) b) A WOCBP who agrees to follow contraceptive guidance during the treatment period and for at least 120 days after the last dose of study treatment.
11. For male patient should agree to use 2 adequate methods of contraception, one of which must be a barrier method, from starting at screening and continue throughout the study period and 120 days after the final dose of study treatment.
12. Ability to swallow tablets without difficulty.
13. Signed and dated written Informed Consent Form by the patient.

6.2. Exclusion Criteria

Patients meeting any of the following criteria must not be enrolled in the study:

1. Has received prior therapy with an anti-PD-1, anti-PD-L1, or anti-PD-L2 agent or an agent directed to another stimulatory or co-inhibitory T-cell receptor (e.g., CTLA-4, OX-40, CD137), any history of discontinuing from that treatment due to Grade 3 or higher immune-related adverse event (irAE).
2. Patient with documented MSI-H status or confirmed by central lab test.
3. Has active autoimmune disease that has required systemic treatment in past 2 years (i.e. with use of disease modifying agents, corticosteroids or immunosuppressive drugs). Replacement therapy (e.g., thyroxine, insulin, or physiologic corticosteroid replacement therapy for adrenal or pituitary insufficiency, etc.) is not considered a form of systemic treatment.
4. History of idiopathic pulmonary fibrosis, organizing pneumonia, drug-induced pneumonitis, idiopathic pneumonitis, (non-infectious) pneumonitis that required steroids, or clinical symptoms of active pneumonitis.
5. Has known active central nervous system (CNS) metastasis and/or carcinomatous meningitis. Patient with previously treated brain metastases may participate provided they are stable (without evidence of progression by imaging at least 4 weeks prior to the first dose of study treatment and any neurologic symptoms have returned to baseline), have no evidence of new or enlarging brain metastases, and are not using steroids for at least 14 days prior to study treatment. This exception does not include carcinomatous meningitis which is excluded regardless of clinical stability.
6. Has a known additional malignancy that is progressing or requires active treatment. Exceptions include basal cell carcinoma or squamous cell carcinoma of the skin that has undergone potentially curative therapy, in situ cervical cancer or any other cancer that has been in complete remission for ≥ 2 years.

7. Patient has had screening echocardiogram (ECHO) or multiplegated acquisition (MUGA) scan performed results in a left ventricular ejection fraction (LVEF) that is < 50%.
8. Significant cardiovascular disease, including myocardial infarction, arterial thromboembolism, or cerebrovascular thromboembolism within 6 months prior to start of study treatment, history of cardiac, carotid, or other major cardiovascular surgery, history of valvular heart disease, symptomatic dysrhythmias or unstable dysrhythmias requiring medical therapy, angina requiring therapy, symptomatic peripheral vascular disease, clinically significant history of syncope, New York Heart Association (NYHA) Class 3 or 4 congestive heart failure, or chronic Grade 3 hypertension (diastolic blood pressure \geq 100 mmHg or systolic blood pressure \geq 160 mmHg).
9. Significant screening electrocardiogram (ECG) abnormalities including atrial fibrillation (unstable or newly diagnosed), double (left and right) bundle branch block, second degree atrioventricular block type II, third-degree atrioventricular block, Grade \geq 2 bradycardia, QTcF interval \geq 450 msec, PR interval $>$ 220 msec, or unstable cardiac arrhythmia requiring medication. Chronic asymptomatic atrial fibrillation stably controlled with medications is permitted.
10. Known family history of sudden cardiac death.
11. Ongoing risk for bleeding due to cancer or bleeding diathesis.
12. Evidence of an ongoing, uncontrolled systemic bacterial, fungal, or viral infection or an uncontrolled local infection requiring therapy at the time of start of study treatment.

Note: Patient with localized fungal infections of skin or nails are eligible.

13. Has a known history of Human Immunodeficiency Virus (HIV) infection or patient who are HIV seropositive. No HIV testing is required unless mandated by local health authority.
14. Current known active infection of Hepatitis B (defined as HBsAg+ and/or HBeAg+) and high titer of HBV DNA or Hepatitis C virus (defined as Anti-HCV and HCV RNA (+)) infection.
15. Diagnosis of immunodeficiency or is receiving chronic systemic steroid therapy (at doses exceeding 10 mg daily of prednisone equivalent) or any other form of immunosuppressive therapy within 14 days prior to the first dose of study treatment.
16. Has received a live or live-attenuated vaccine within 30 days of planned start of study treatment.

Note: Administration of killed vaccines are allowed.

17. Has had an allogeneic tissue/solid organ transplant.
18. Males who plan to father children within the projected duration of the study, starting with the screening visit through 120 days after the final dose of study treatment.
19. Major surgery within 28 days (or inadequate recovery from the toxicity or complications of the intervention) before the start of study treatment.

Note: If the participant had major surgery, the participant must have recovered adequately from the procedure and/or any complications from the surgery prior to starting study intervention.

20. Radiotherapy within 14 days of start of study treatment. Patient must have recovered from all radiation-related toxicities, not require corticosteroids, and not have had radiation pneumonitis. A 7-day washout is permitted for palliative radiation (i.e., \leq 14-day course of radiotherapy) to non-CNS lesions.
21. Patient currently receiving treatment with any medications that have the potential to prolong the QT interval and that cannot be either discontinued or substituted with a different medication prior to starting study treatment.

22. Patient currently receiving treatment with strong cytochrome P450 (CYP)3A4 inhibitors or inducers should discontinue such treatment or be switched to a different medication prior to starting study treatment.
23. Current participations in another study of an investigational agent or investigational device within 4 weeks prior to the first dose of study.
24. Any illness, medical condition, organ system dysfunction, or social situation, including mental illness or substance abuse, deemed by the investigator to be likely to interfere with a patient's ability to sign informed consent, adversely affect the patient's ability to cooperate and participate in the study, or compromise the interpretation of study results.

7. TREATMENT

7.1. Dose Rationale for Combination Therapy

[REDACTED]

[REDACTED]

[figure not shown]
[figure not shown]
[REDACTED]

[REDACTED]

[REDACTED]

[REDACTED]

[REDACTED]

7.1.2. Pembrolizumab

The planned dose of Pembrolizumab (Keytruda®) for this study is 200 mg every 3 weeks (Q3W), which is the currently approved dosage for treatment of advanced cancer. Based on the totality of data generated in the Keytruda development program, 200 mg Q3W is the appropriate dose of pembrolizumab for adults across all cancer indications. This dose is justified by:

- Clinical data from 8 randomized studies in melanoma and NSCLC indications that demonstrated flat dose- and exposure efficacy relationships from 2 mg/kg Q3W to 10 mg/kg every 2 weeks (Q2W) representing an approximate 5 to 7.5 fold exposure range (refer to the IB).
- Population PK analysis showed that both fixed dosing and weight-based dosing provides similar control of PK variability with considerable overlap in the distributions of exposures, supporting suitability of 200 mg Q3W.
- Clinical data that showed meaningful improvement in benefit-risk, including overall survival (OS) at 200 mg Q3W across multiple indications.
- Pharmacology data that showed full target saturation in both systemic circulation (inferred from pharmacokinetic [PK] data) and tumors (inferred from physiologically based PK [PBPK] analysis) at 200 mg Q3W.

Among the eight randomized, dose-comparison studies, 2262 patients were enrolled with melanoma and NSCLC, covering different disease settings (treatment naïve, previously treated, PD-L1 enriched, and all-comers) and different treatment settings (monotherapy and in combination with chemotherapy). Five studies compared 2 mg/kg Q3W versus 10 mg/kg Q2W (KN001 Cohort B2; KN001 Cohort D; KN002; KN010; and KN021) and 3 studies compared 10 mg/kg Q3W versus 10 mg/kg Q2W (KN001 Cohort B3; KN001 Cohort F2; KN006). All of these studies demonstrated flat dose- and exposure-response relationships across the doses studied, representing an approximate 5- to 7.5-fold difference in exposure. The 2 mg/kg (or 200 mg fixed dose) Q3W dosages provided similar responses to the highest doses studied. Subsequently, flat-dose exposure-response relationships were also observed in other tumor types, including HNSCC, bladder cancer, gastric cancer, and classical Hodgkin lymphoma, confirming 200 mg Q3W as the appropriate dose independent of tumor type. These findings are consistent with the mechanism of action of pembrolizumab, which acts by interaction with immune cells, and not via direct binding to cancer cells.

Additionally, pharmacology data for pembrolizumab show target saturation at 200 mg Q3W. First, PK data in KN001 evaluating target-mediated drug disposition conclusively demonstrated saturation of PD-1 in systemic circulation at doses much lower than 200 mg Q3W. Second, a PBPK analysis was conducted to predict tumor PD-1 saturation over a wide range of tumor penetration and PD-1 expression. This evaluation concluded that pembrolizumab at 200 mg Q3W achieves full PD-1 saturation in both blood and tumor.

Finally, population PK analysis of pembrolizumab, which characterized the influence of body weight and other subject covariates on exposure, has shown that fixed dosing provides similar control of PK variability as weight-based dosing, with considerable overlap in the distribution of exposures from the 200 mg Q3W fixed dose and 2 mg/kg Q3W dose. Supported by these PK characteristics and given that a fixed dose has advantages of reduced dosing complexity and reduced potential of dosing errors, the 200 mg Q3W fixed dose was selected for evaluation across all pembrolizumab protocols.

Refer to the approved labeling and Investigator's Brochure for more details on Keytruda® (Pembrolizumab, MK-3475) (Keytruda Investigator's Brochure).

7.1.3. Selection of Doses in the study

Based on the cumulative PK, PD, and safety data in healthy volunteers (FLX475-01 Ph1 study), and in patients with advanced cancer (Phase 1 portion of the ongoing FLX475-02 Phase 1/2 study), a recommended Phase 2 dose of 100 mg QD for FLX475 in combination with standard dose pembrolizumab has been selected.

The dose of pembrolizumab used in this study, 200 mg as a 30-minute IV infusion Q3W, is the approved dosage in advanced cancer, based on clinical data from 8 randomized studies.

7.2. Overview of Treatments Administered

Subjects will take FLX475 orally once daily (QD) starting on Day 1 of Cycle 1 and in conjunction with pembrolizumab 200 mg by IV Q3W. Subjects should maintain a normal diet unless modifications are required to manage an AE such as diarrhea, nausea, or vomiting. Fasting is not required for FLX475 administration.

The treatments to be used in this study are outlined in Table 7.2:1.

Table 7.2:1 Study Treatments

Study Treatment	Formulation	Dose	Route of Administration	Sourcing
FLX475	Tablets	100mg, QD	Oral	Provided centrally by the Sponsor
Pembrolizumab	Solution for infusion	200 mg, Q3W	IV infusion	Provided centrally by the Sponsor

IV = intravenous, Q3W = once every 3 weeks, QD = once daily.

7.2.1. FLX475 Administration

FLX475 tablets are to be taken with water orally once a day at approximately the same time each day in every 3-week cycle (21 days) from Cycle 1 Day 1 onward. Fasting is not required for FLX475 administration. On days when a clinic visit, the dose of FLX475 will be administered in the clinic after the specified visit assessments and procedures are performed.

FLX475 should be taken approximately 1 hour before the pembrolizumab infusion, on days when pembrolizumab is also administered (i.e., Day 1 of each cycle).

The dose modification for FLX475 is provided in Section 7.3

7.2.2. Pembrolizumab Administration

Pembrolizumab 200 mg will be administered as an IV infusion over 30 minutes on Day 1 of every 3-week treatment cycle (i.e., every 21 days [± 3 days]) after all procedures and assessments have been completed, and approximately 1 hour after the Day 1 dose of FLX475.

The site staff should make every effort to ensure that the infusion duration be as close to 30 minutes as possible. However, given the variability of infusion pumps from site to site, a window between -5 minutes and +10 minutes is permitted (i.e., infusion time of 25 to 40 minutes).

The Pharmacy Manual contains specific instructions for the preparation and administration of the pembrolizumab infusion.

7.3. Dose Modification

Dose modifications and drug discontinuation may be acceptable for toxicity but should be implemented at the investigator's discretion in consultation with the sponsor or medical monitor after considering the subject's condition and the clinical benefit to the subject of continuing treatment at the current dose.

The investigator will decide whether any AE that occurs is related to either or both drugs and determine whether dose modification or discontinuation of one or both drug is required per the guidance below.

7.3.1. FLX475

For subjects receiving study treatment, the following dose modification and discontinuation guidelines must be followed:

- The investigator may interrupt treatment with FLX475 for any other AE considered unacceptable for the individual subject, and treatment may be resumed at the next lower dose level when resolved to Grade 0 or 1 or to pretreatment severity grade.
- If no lower dose level exists to which the subject may de-escalate, FLX475 should be discontinued.

Other dose modifications may be acceptable but should be implemented at the investigator's discretion in consultation with the medical monitor, considering the subject's condition and the clinical benefit to the subject of continuing treatment at the current dose.

If the subject requires a dose modification for an AE, then FLX475 administration should be interrupted, as necessary, until the AE resolves or stabilizes to an acceptable degree (generally to CTCAE(v5.0) Grade 0 or 1 or to pretreatment severity grade). Thereafter, treatment with FLX475 may be reinstated at the next lower dose level. Subsequent reductions to successively lower dose levels can be made, if needed, as shown in Table 7.3:1 More frequent laboratory monitoring may be required.

Once the dose of study treatment has been reduced, it may not be increased at a later date, unless the dose was mistakenly decreased; in this situation, the Sponsor or medical monitor's approval is required to increase the dose.

Table 7.3:1 Dose Modification Guidelines for FLX475-related Toxicity

Grade (CTCAE v5.0)	Treatment-Related Toxicity ^{a, b}			
	First occurrence	Second occurrence (same toxicity or new toxicity)	Third occurrence (same toxicity or new toxicity)	Fourth occurrence
Grade 1 or Tolerable Grade 2	Continue Treatment			
Intolerable Grade 2 ^{c, d} or Grade 3 ^{e, f}	
 ♦ Management: Interrupt FLX475 until resolved to Grade 0-1 or tolerable Grade 2 (or baseline) ♦ Dose Adjustment: Reduce FLX475 dose by 1 level (75mg) 	
 ♦ Management: Interrupt FLX475 until resolved to Grade 0-1 or tolerable Grade 2 (or baseline) ♦ Dose Adjustment: Reduce FLX475 dose by lower level (50mg) 	
 ♦ Management: Interrupt FLX475 ♦ Dose Adjustment: Discuss with Sponsor (permanently discontinue from FLX475 treatment or to be in the subject's best interest to continue treatment, at a reduced dose) 	N/A
Grade 4 ^g	Discontinue Study Treatment			

Guide for Related Adverse Events					
Grade (CTCAE v5.0)		First occurrence	Second occurrence (same toxicity or new toxicity)	Third occurrence (same toxicity or new toxicity)	Fourth occurrence
Any drug-related AE (neurologic, pulmonary, cardiac, gastrointestinal, genitourinary, renal, hepatic, cutaneous)		Grade 4	Permanently discontinue (Unless it is determined by the investigator, in consultation with the Sponsor or medical monitor, to be in the subject's best interest to continue treatment, at a reduced dose)		
Gastrointestinal (GI) tract	Grade 3	Withhold FLX475 treatment until AE Grade ≤ 1 (or to pretreatment severity grade) and then resume treatment at reduced dose: 100 mg \rightarrow 75 mg	Withhold FLX475 treatment until AE Grade ≤ 1 (or to pretreatment severity grade) and then resume treatment at reduced dose: 75 mg \rightarrow 50 mg	Permanently discontinue from FLX475 treatment	N/A
AST / ALT elevation or Increased bilirubin	Grade 3	Withhold FLX475 treatment until AE Grade ≤ 1 (or to pretreatment severity grade) and then resume treatment at the reduced dose: 100 mg \rightarrow 75 mg	Withhold FLX475 treatment until AE Grade ≤ 1 (or to pretreatment severity grade) and then resume treatment at reduced dose: 75 mg \rightarrow 50 mg	Permanently discontinue from FLX475 treatment	N/A

Guide for Related Adverse Events				
Grade (CTCAE v5.0)	First occurrence	Second occurrence (same toxicity or new toxicity)	Third occurrence (same toxicity or new toxicity)	Fourth occurrence
QTcF prolongation ^h	Grade 1	No dose reduction is required		
	Grade 2 (≤ 6 hours after FLX475 dose)			
	Grade 2 or 3 (immediately prior to or > 6 hours after FLX475 dose)	Withhold FLX475 treatment until AE Grade ≤1 (or to pretreatment severity grade) and then resume treatment at reduced dose: 100 mg → 50 mg	Permanently discontinued from FLX475 treatment (at 50 mg or lower dose level) or continue treatment either at 50 mg or at a reduced dose of 25 mg (If it is determined by the investigator, in consultation with the Sponsor or medical monitor, to be in the subject's best interest)	N/A

Guide for Related Adverse Events					
Grade (CTCAE v5.0)		First occurrence	Second occurrence (same toxicity or new toxicity)	Third occurrence (same toxicity or new toxicity)	Fourth occurrence
	Grade 3 (≤ 6 hours after FLX475 dose)	Withhold FLX475 treatment until AE Grade ≤1 (or to pretreatment severity grade) and then resume treatment at reduced dose: 100 mg → 50 mg	Permanently discontinued from FLX475 treatment (at 50 mg or lower dose level) or continue treatment either at 50 mg or at a reduced dose of 25 mg (If it is determined by the investigator, in consultation with the Sponsor or medical monitor, to be in the subject's best interest)	N/A	N/A
	Grade 4	Should be treated appropriately and permanently discontinued from FLX475 treatment (unless it is later determined by the investigator, in consultation with the Sponsor or medical monitor, to be in the subject's best interest to continue treatment)			

Note: For grading see CTCAE version 5.0. Collect all CTC grades of adverse events, decreasing and increasing grade.

BMI = body mass index, CTCAE = Common Terminology Criteria for Adverse Events.

- An interruption of study treatment for more than 21 days will require Sponsor's approval before treatment can be resumed.
- Initiate optimal medical management for nausea, vomiting, hypothyroidism and/or diarrhea prior to any study treatment interruption or dose reduction.

- c. Applicable only to Grade 2 toxicities judged by the subject or physician to be intolerable.
- d. Obese subjects with weight loss do not need their weight to return to baseline weight or within 10% of baseline weight (i.e., Grade 1 weight loss). These subjects will restart the study treatment(s) at a lower dose once their weight remains stable for at least 1 week and they reach their normal BMI (if the weight loss occurs but is still above normal BMI, they can restart study treatment at a lower dose once their weight has been stable for at least 1 week). Normal BMI should be used as the new baseline for further dose reductions.
- e. For Grade 3 toxicity, investigator will decide the probability of the event being related to 1 or both drugs and as to whether dose modification of either or both drugs is required.
- f. For asymptomatic laboratory abnormalities, such as Grade ≥ 3 elevations of amylase and lipase that are not considered clinically relevant by the investigator, continuation of treatment should be discussed with the Sponsor.
- g. Excluding laboratory abnormalities judged to be non-life-threatening, in which case manage as Grade 3.
- h. Any subjects with observed QTcF prolongation of potential significance should have the ECG repeated for confirmation and electrolytes assessed and replaced as needed prior to action with study drug being taken. An average of QTcF values from triplicate ECGs and NOT an individual QTcF value from a single ECG should be used for dose modification considerations.

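### Table 7.3:1 gives FLX475 instructions in two overlapping blocks with no stated precedence; they differ on whether a related Grade 4 event allows an exception to stopping

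*Protocol*

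**What the plan says.** Protocol 7.3.1 introduces its rules as binding: "the following dose modification and discontinuation guidelines must be followed". Protocol 7.4 then makes FLX475 discontinuation mandatory for any toxicity that 7.3.1 lists as a reason for permanent discontinuation.

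Table 7.3:1 has two parts. The first is a general block organised by CTCAE grade and number of occurrences. The second, the Guide for Related Adverse Events, has rows for any drug-related AE at Grade 4, for Grade 3 GI events, for Grade 3 AST/ALT/bilirubin events and for QTcF prolongation.

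**Grade 4**
- The general row says "Discontinue Study Treatment". Its footnote g reads "Excluding laboratory abnormalities judged to be non-life-threatening, in which case manage as Grade 3".
- The row for any drug-related AE says "Permanently discontinue (Unless it is determined by the investigator, in consultation with the Sponsor or medical monitor", and goes on to permit continuing at a lower dose if that is in the subject's best interest.
- The QTcF row calls for permanent discontinuation of FLX475, "unless it is later determined by the investigator, in consultation with the Sponsor or medical monitor", that continuing is in the subject's best interest. It mentions no dose reduction.

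**Third occurrence of a Grade 3 event**
- The general row sends the case to the Sponsor, with either discontinuation or a reduced dose as the outcome.
- The GI and AST/ALT/bilirubin rows say "Permanently discontinue from FLX475 treatment".

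**Recovery before restart**
- The general row says "Interrupt FLX475 until resolved to Grade 0-1 or tolerable Grade 2 (or baseline").
- The GI and AST/ALT/bilirubin rows ask for Grade 1 or below, or the pretreatment grade.

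**The concern.** A table that must be followed should give one answer for one clinical situation. Here a single related event can fall under two rows that grant different latitude, and a site has no rule for choosing between them. The choice matters because 7.4 turns a permanent-discontinuation entry into a mandatory stop. Whether the stop is absolute, or open to a best-interest exception, depends on the row read.

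Two things are at stake. The first is consistent safety management after the most severe related toxicities. The second is interpretation of the safety outputs. SAP 8 summarises dose modification and relative dose intensity, and SAP 13.1 tabulates TEAEs leading to dose modification and to discontinuation. Those summaries would partly reflect which row was applied. The IDMC's first look comes at 10 subjects per cohort (Protocol 11.5), so a few inconsistent decisions would be visible there. Protocol 17.4 carries Section 7.3 into the extension part, so the ambiguity continues after the main study.

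**Working it through.** No arithmetic applies. The check sets the overlapping instructions side by side and asks whether anything in the documents ranks them.

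| Situation | General block | Guide for Related Adverse Events | Same instruction? |
|---|---|---|---|
| Related Grade 4 event, not QTcF | Stop; no best-interest exception | Stop, unless continuing at a lower dose is agreed after consultation | Same default; exception in one row only |
| Related Grade 4 QTcF event | Stop; no best-interest exception | Stop FLX475, unless continuing is later agreed; no reduction mentioned | Same default; exception in one row only |
| Third related Grade 3 GI or AST/ALT/bilirubin event | Discuss with Sponsor; stop or reduce | Permanent stop, no exception | No |
| Grade 3 GI or AST/ALT/bilirubin event now at tolerable Grade 2, baseline Grade 0 | Restart condition met | Restart condition not met | No |

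**Step 1: is the Grade 4 difference removed by a footnote?** Footnote g exempts only laboratory abnormalities judged non-life-threatening. Footnote f is marked on the Grade 3 row, but its text reaches asymptomatic laboratory abnormalities of Grade 3 or above that the investigator considers not clinically relevant, and refers them to the Sponsor. Both concern laboratory values. Neither gives the general Grade 4 row an exception for a clinical event.

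**Step 2: does specific over general settle Grade 4?** The second-block row is worded for any drug-related AE and lists neurologic, pulmonary, cardiac, gastrointestinal, genitourinary, renal, hepatic and cutaneous events: eight systems. That is about as broad as the general row. If it always prevailed, the unconditional stop would have almost no remaining use. Breadth therefore does not show which row was meant to govern.

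**Step 3: does the difference run in one direction only?** No. Take a non-life-threatening Grade 4 hepatic laboratory value reported as a drug-related AE. Footnote g handles it as Grade 3, while the any-AE row makes permanent discontinuation the default. Here the general block is the more permissive one.

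**Step 4: do the rows name the same drugs?** The general row refers to study treatment, which Protocol 7.5 identifies as FLX475 and pembrolizumab. The QTcF row names FLX475 alone, and Protocol 8.2 allows pembrolizumab to continue alone in some cases. The extent of the stop is thus also open.

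**Step 5: how far do the Grade 3 mismatches extend?** Only to GI and AST/ALT/bilirubin events, the non-QTcF toxicities with their own Grade 3 rows. Other non-QTcF toxicities meet only the general row. The QTcF rows follow a separate scheme with their own timing and dose steps.

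**Step 6: is precedence stated anywhere?** No such sentence appears in 7.3, in 7.3.1 or its footnotes, or in 7.4.

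**The case against.** The strongest reply is that a reader might infer the Grade 4 rows give opposite orders, and they do not. All three default to discontinuation. Two spell out an exception that requires consultation with the Sponsor or medical monitor. The Section 7.3 preamble also says that modification and discontinuation are at the investigator's discretion in consultation with the sponsor or medical monitor, and 7.3.1 repeats this for other dose modifications. This stands: the difference is between a default and the same default with an exception. It does not close the point, because the discretion clause sits beside wording that the guidelines must be followed and names no governing row.

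A reader might also infer that sites could diverge freely. The documents do not support that. Continuing after Grade 4, or at a general-row third occurrence, involves the Sponsor or medical monitor, and resuming after more than 21 days' interruption needs Sponsor approval. Central involvement limits divergence, although those advising still have no stated precedence to apply.

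For the Grade 3 GI and AST/ALT/bilirubin rows, reading specific over general is plausible and would resolve the row-against-row mismatch. It is simply not stated. The 7.3.1 text on recovery is qualified as general guidance, so its difference from the general row's tolerable Grade 2 is soft.

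Finally, "If no lower dose level exists to which the subject may de-escalate, FLX475 should be discontinued" might be taken to contradict the general row's third-occurrence option. The sentence is conditional, and 25 mg is named in the QTcF rows. Whether that level is available for other toxicities is an open question, not a demonstrated contradiction.

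**Conclusion.** The point holds as an internal inconsistency in a mandatory safety table. The main part is Grade 4: one row has no best-interest exception, while the similarly broad any-AE row and the QTcF row each have one, and nothing ranks them. The secondary part is limited to Grade 3 GI and AST/ALT/bilirubin events, at the third occurrence and at restart.

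The size cannot be given as a count, because the documents provide no expected rate of related Grade 4 or recurrent Grade 3 events. The conclusion rests on the table text as it stands and on the absence of any precedence sentence in the protocol.

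A reader might infer damage to the efficacy conclusions. The documents do not support that. ORR is analysed in all subjects dosed (SAP 4.1.1), no formal testing is planned (SAP 2.4), and the exposure and adverse-event outputs are descriptive. The effect is on consistent safety management and on how the dose-modification and discontinuation summaries are read.

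**What to change.** The sponsor's clinical team should reconcile the general block, the Guide for Related Adverse Events, footnotes f and g and the 7.3.1 text, so that each situation has one instruction. They should state which block takes precedence where two rows apply. The reconciled text should cover at least:
- related Grade 4 events, including QTcF and laboratory-only events, and which drug or drugs the stop covers;
- the third occurrence of a Grade 3 GI or AST/ALT/bilirubin event;
- the recovery grade required before restart for those same events.

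Which clinical rule is right is for that team and is not proposed here.

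The cost is a protocol clarification, issued as a formal amendment under Protocol 14.5. It needs no change to sample size, endpoints or the SAP analyses, and it carries into the extension part through 17.4.
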